## **CONDITIONS FOR TERMINATION**

### **1. Discontinuing patients from the study**

Every effort will be made to keep the patient on the research study. However, in the event that a patient is withdrawn from the research study, the investigator should document the reasons for withdrawal as thoroughly as possible and notify the PI. This evaluation should include final observations, as required by the research protocol at the time of the patient's withdrawal. The reason(s) for early termination must be clearly documented on the appropriate page of the patient's case report form (CRF). A CRF must be completed for any patient who receives ANY amount of treatment on this research study.

#### Criteria for Early Termination of Treatment under this Research Protocol

- 1) Significant deviation from the research protocol or eligibility criteria. Such patients will be considered protocol violations and will be removed from research study.
- 2) Patients who develop a concurrent illness, which, in the opinion of the investigator, would prevent their safe completion of treatment or required research study-related evaluations.
- 3) Patients who are non-compliant with the research study or follow-up procedures.
- 4) Patients who withdraw consent and elect to terminate their participation in the research study.

- 5) The occurrence of a grade 3 or greater hematologic toxicity, persisting 7 days or longer according to NCI CTCAE VERSION 4.03.
- 6) Termination of the research study by the Sponsor.

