**Follow-up (Patient Flow Chart, page 28)**

**Office visits**

Office visits with neurologic evaluation will be performed at one, six, twelve, and twenty-four months after treatment. At this time the patients will also fill the Tinnitus Handicap Inventory Questionnaire. The visits will last about 45 minutes.

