**Follow-up Information on an SAE:**

Appropriate diagnostic tests should be performed and therapeutic measures, if indicated, should be instituted. Appropriate consultation and follow-up evaluations should be carried out until the event has resolved or is otherwise explained. Follow-up data concerning the SAE (e.g., diagnostic test reports, physician's summaries, etc.) will also be submitted.

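### Removing stented patients from the study after a significant deviation ends the 12-month and 24-month follow-up the trial needs

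*Protocol*

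**What the plan says.** The rule is item 1 of a list headed "Criteria for Early Termination of Treatment under this Research Protocol" (Protocol, Conditions for Termination). It covers a significant deviation from the protocol or from eligibility, and its consequence is stated for the study, not for treatment: "Such patients will be considered protocol violations and will be removed from research study". The word significant is not defined. Item 3 of the same list names "Patients who are non-compliant with the research study or follow-up procedures".

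The section just above it, on discontinuing patients, points the other way: "Every effort will be made to keep the patient on the research study". For a patient who is withdrawn it asks for reasons and an evaluation: "This evaluation should include final observations, as required by the research protocol", taken at the time of withdrawal. It adds: "A CRF must be completed for any patient who receives ANY amount of treatment on this research study".

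The follow-up at stake is set out elsewhere in the protocol:

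- Office visits: "Office visits with neurologic evaluation will be performed at one, six, twelve, and twenty-four months after treatment", with the Tinnitus Handicap Inventory (THI) completed at each.
- Imaging studies: an MR venogram (MRV) at 12 months, or a CT venogram if MRV is contraindicated.
- Secondary Outcomes and Secondary Endpoints: related adverse events over 24 months.
- Primary Outcome: the 12-month result, with a target of more than 75% among treated patients.
- Data Analysis: reporting covers everyone enrolled.
- Number of Patients: 20.

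**The concern.** The list treats ending treatment and leaving the study as one act. The stent is deployed in a single procedure, and afterwards only antiplatelet therapy continues. Removing a stented patient therefore does little to the treatment already given but cuts off its observation. A 12-month grade or venogram that was never obtained cannot be supplied later by any analysis plan, so this belongs to the protocol.

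The stakes are higher because the trial is small, single-arm and concerns an implant. Each early removal costs one primary grade and one patency result out of at most 20, and shortens the watch for device-related events in someone who still carries the device. The loss may also be related to outcome. The section Other treatments expects patients to stop all earlier tinnitus treatments; a patient whose tinnitus persists and who resumes one could be classed as a significant deviation and removed. That example is an inference, since the term is undefined.

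**Working it through.** **1. What survives removal.** Each provision that might keep the data was set against item 1.

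- Final observations at withdrawal give one assessment on that date. It is not the 12-month grade or venogram unless the dates coincide.
- Follow-up Information on an SAE: "Appropriate consultation and follow-up evaluations should be carried out until the event has resolved or is otherwise explained". This concerns an event that has already occurred and does not detect one that starts later.
- Reporting on all enrolled patients governs data already held.
- The CRF has fields for grades at 1, 6, 12 and 24 months and for the 12-month MRV. Fields do not order visits for a patient who has left.

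No provision schedules assessments after removal. Equally, none says that removed patients leave the denominator.

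**2. Inputs for size.** N = 20 (Number of Patients), all assumed stented. Target above 75% of treated patients (Primary Outcome). The protocol states no removal rate and no figure that could be reproduced. Assumed: k = 1 or 2 removals before month 12, unrelated to outcome. Assumed true success rate p = 0.93, 0.90 or 0.85. The first borrows the 93/100 resolved in the literature summary (Hypothesis and Objectives), which is not the same endpoint as the 12-month THI grade.

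**3. Primary proportion.** 0.75 × 20 = 15, so more than 75% needs at least 16 successes. Each missing grade is worth 1/20 = 5 points. With k missing and s successes seen among 20 − k, the target is undecided when s < 16 but s + k ≥ 16.

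- k = 1: s = 15 of 19, probability P(Bin(19, p) = 15).
- k = 2: s = 14 or 15 of 18, probability P(Bin(18, p) = 14 or 15).

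| p | k = 1 | k = 2 |
|---|---|---|
| 0.93 | 0.031 | 0.121 |
| 0.90 | 0.080 | 0.238 |
| 0.85 | 0.171 | 0.400 |

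**4. Adverse-event observation.** Planned total: 20 × 24 = 480 patient-months. One removal at month m loses (24 − m)/480:

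- m = 1: 23/480 = 4.8%
- m = 6: 18/480 = 3.8%
- m = 12: 12/480 = 2.5%

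Removal after the month-12 assessments costs neither the primary grade nor the MRV.

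**5. Could the result flip?** Only if removed patients were also dropped from the denominator and were non-responders, which the protocol nowhere states. One such removal would turn 15/20 = 75.0% into 15/19 = 78.9%; two would turn 14/20 = 70.0% into 14/18 = 77.8%. The chance of 14 or 15 successes in 20 is 0.010 at p = 0.93 and 0.041 at p = 0.90, so a flip is unlikely.

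**The case against.** The strongest reply is that the loss is inferred. The protocol does not say that collection stops. It wants patients kept, and it requires a CRF for anyone treated; that CRF has fields out to 24 months. One could read these together as continuing follow-up. This shows ambiguity, but the CRF could equally be completed only up to withdrawal, and a site applying a mandatory removal rule would probably do that. Because the protocol foresees withdrawals, this is a tension between sections and not a flat contradiction.

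Second, exposure may be small. Much of eligibility is settled before implantation, by ENT work-up, imaging, venography and manometry, and a patient removed at those steps has no stent follow-up to lose. The probabilities above are also conditional on a removal having happened. If each patient had an independent removal risk r, the unconditional chance of an undecided target is the sum over k of P(Bin(20, r) = k) times the conditional probability for k. For r = 1%, 2% and 5% this gives about 0.007, 0.017 and 0.066 at p = 0.93, and 0.017, 0.038 and 0.118 at p = 0.90. This stands: the frequency is unknown and could be zero. It limits the size, not the defect.

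Third, the 75% target is descriptive, since the protocol plans proportions without a test. That is so, but the proportion and the patency result would still have holes.

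Fourth, keeping a patient who has resumed another tinnitus treatment blurs the effect of stenting alone. That can be dealt with at analysis if the data exist.

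**Conclusion.** The point holds and should be fixed. Followed as written, item 1 ends whatever 12-month THI, 12-month MRV and new adverse-event collection is still due for a stented patient with a significant deviation. Each removal before month 12 costs 5 points of certainty on the primary proportion, and one removal at month 1 costs 4.8% of the planned adverse-event observation.

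Confidence is medium. The conclusion rests on reading removed in its ordinary sense; the size rests on assumed numbers of removals, all 20 patients being stented, and removals unrelated to outcome. It is not claimed that removed patients are dropped from the analysis or that the trial's conclusion would probably change.

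**What to change.** In item 1, replace removal from the study with wording to this effect: *the deviation is recorded; a stented patient remains in scheduled follow-up to 24 months (office visits with THI, 12-month imaging, adverse events) unless consent is withdrawn.* At item 3, add that non-compliance does not by itself end attempts to collect these data. The change concerns data collection only; whether any treatment stops is a separate matter and is left alone.

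The cost is one sentence and one clause, with no visits beyond those already scheduled. Per retained patient it is at most four office visits of about 45 minutes (4 × 45 = 180 minutes) and one MRV. The three-month audiometry is not an endpoint and is not needed for this repair. The downside is that patients who do not attend may still give no data, so the change reduces the loss without removing it.

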## **2. Study termination**

The study will be discontinued if a serious adverse event (SAE) that is unexpected and protocol-related occurs in more than two of the first five or more than three of the first ten procedures.

## **STUDY MONITORING**

The study will be monitored by the Weill Cornell Medical College Data Safety Monitoring Board (WCMC DSMB).

Data Safety Monitoring Board  
[name]  
[contact]  
[contact]  
E-mail: [[contact]](mailto:[contact])

Adverse events will be reported to the WCMC DSMB according to the same policies as they will be reported to the FDA and WCMC IRB:

### **Reporting SAEs, Unexpected Adverse Experiences, and Patient Deaths**

#### **1. Time-frame for Reporting:**

Any harm experienced by a participant related to the research procedure, intervention, and/or device when **ALL** of the following three (3) conditions are met will be reported within 7 calendar days:

1. The harm is “unexpected” when its specificity and severity are not accurately reflected in the WCMC consent document and protocol **AND**

2. The harm is “related or possibly related”, where there is a reasonable possibility that the harm may have been caused by the research procedure or intervention **AND**
3. The harm suggests that the research places subjects at greater risk of harm (including physical, psychological, economic or social harm) than was previously known or recognized

In addition to the above, any unanticipated adverse effect (any serious adverse effect on health or safety or any life threatening problem or death) will be reported within 7 calendar days that is **EITHER**:

1. Caused by, or associated with, a device if that effect, problem, or death was not previously identified in nature, severity, or degree of incidence in the investigational plan or IDE application (including a supplementary plan or application); **OR**
2. Any other unanticipated serious problem associated with a device that relates to the rights, safety, or welfare of participants.

**2. Information to be provided by the Investigator**

At the time of the report, the investigator must transmit information regarding the following:

- Underlying diagnosis and extent of disease
- Dates of procedure
- Description of event, including date of onset and duration
- Date of death (if applicable)
- Intervention(s) required
- Concomitant therapy (including regimen(s) and indication)
- Pertinent laboratory data/diagnostic test (including dates)
- Pertinent medical history
- Severity of the adverse experience
- Relationship of the adverse experience to research study treatment

- Outcome of the adverse experience

In addition, a cumulative list of unexpected AEs and serious AEs will be reported after every 5 patients, as determined by the WCMC DSMB. Detailed, narrative descriptions of each AE from the last report will accompany the cumulative list.

REFERENCES

**Patient Flow Chart**

**PRINT OUT OF ELECTRONIC CASE REPORT FORM**

Name: \_\_\_\_\_

Age: \_\_\_\_\_

DOB: \_\_\_\_\_

MRN: \_\_\_\_\_

Tinnitus Grade:  0  
 1  
 2  
 3  
 4  
 5Tinnitus Location:  Right  
 Left  
 BilateralVenous Dominance:  Right  
 Left  
 CodominantStenosis Location:  Right  
 Left  
 Bilateral

Stenting Date: \_\_\_\_\_

Stenting Result:  no residual stenosis  
 residual stenosis <50%  
 residual stenosis >50%  
 technical failure

Adverse Events:

- Serious
- Non-serious
- Unexpected

Description of Adverse Event

---

---

---

---

Tinnitus Grade:  0

Post-Stent (1 month)  1  
 2  
 3  
 4  
 5

Tinnitus Grade:  0

Post-Stent (6 mos)  1  
 2  
 3  
 4  
 5

Tinnitus Grade:  0

Post-Stent (12 mos)  1  
 2  
 3  
 4  
 5

Tinnitus Grade:  0

Post-Stent (24 mos)  1  
 2  
 3  
 4  
 5

MRV (12 mos)

- no residual stenosis or thrombosis
- in-stent stenosis <50%
- in-stent stenosis >50%
- new stenosis
- stent thrombosis

Any procedure-related adverse event after 24 months

---

---

---

---

**MANUFACTURING INFORMATION**

We (the sponsors) do not have access to the manufacturing information of the device. In a letter attached to this application, the manufacturer (Cordis Corporation) grants FDA the permission to reference the files used for the PMA#030047 in its review for the application for IDE# G090050.

## **INVESTIGATOR INFORMATION**

All participating investigators and the monitor are listed below. All investigators have signed the agreement and no other investigator will be added until the agreement is signed.

**Updated IDE; May 12, 2017, Page: 38**

**SALES INFORMATION**

The device will not be sold or commercialized.

**LABELING**

We will use the standard device labeling as approved by the FDA for carotid stenting.
